- Global change – The abbreviated CSR will focus on reporting safety endpoints as there were too few patients who received AZD2811 in combination with durvalumab (9 patients) to give meaningful analyses. The efficacy analyses will be streamlined and this will be fully documented in the SAP.
- Table 2 and Table 4 – Addition of +/- 1 week to the Follow-up visit.
- Section 9.4.6 – [CC1] [REDACTED]
- Administrative changes for clarity and consistency throughout.

Version 8, 10 December 2021 (Amendment 7)

- Introduced global changes to align with the Dear Investigator Letter, dated 11 October 2021.
- Administrative changes for clarity and consistency throughout.
- Global change- Changed maximum starting dose of AZD2811 in the Maintenance Phase to [CC1] (previously [CC1]) and added that the study aims to achieve 80 evaluable participants on the starting dose of [CC1].

- Global change- Added that if short-acting G-CSF is used, it should be administered daily until at least [CC1] of each cycle and until the ANC has recovered to $\geq 1.5 \times 10^9/L$.
- Global change- Clarified that where possible, every effort should be made to schedule the scan within 1 week prior to dosing with AZD2811; scan results must be reviewed prior to dosing to confirm the absence of disease progression
- Synopsis- Updated to align with changes in main body of CSP.
- Table 1- Clarified CT scan to be performed during [CC1] scan, to confirm eligibility for maintenance phase.
- Table 1 and Table 3- [CC1]
[REDACTED].
- Table 2- Added that an AE/SAE assessment is required every 2 months +/-1 week after the 90 day follow-up for participants not entering the maintenance phase.
- Table 3, Section 4.1.2.1, and Section 5.3- Added that eligibility criteria for the maintenance phase must be confirmed prior to dosing with AZD2811.
- Table 3 – Added mandatory assessments on Day 12 of Cycle 5 and Cycle 6: vital signs; concomitant medications; AE/SAE assessment; hematology; and blood sample for AZD2811 PK (postdose).
- Table 3- Clarified that a blood sample for durvalumab PK (predose) is not required beyond Day 1 of Cycle 7.
- Table 3- [CC1]
[REDACTED]
- Table 3, Section 4.1, and Section 8.1- Clarified when RECIST v1.1 tumor assessments should be performed and that these scans must be reviewed prior to dosing of AZD2811.
- Table 3 and Section 7.1- Clarified that for participants receiving durvalumab monotherapy, only Day 1 visits and assessments must be completed.

- Table 3 and Table 5- Removed text stating ‘G-CSF must be discontinued 48 hours prior to the next dose of AZD2811. Complete blood counts should be collected and reviewed on Day 8 and/or Day 15.’ These details can be found in Section 6.2.4.
- Table 4- Specified that, for several samples, blood does not need to be drawn for participants who received re-treatment after relapse.
- Table 6- Updated sepsis to be an identified risk, rather than a potential risk, associated with AZD2811.
- Table 6- Updated pancreatitis and encephalitis to be identified risks, rather than potential risks, associated with durvalumab.
- Table 6- Removed non-infectious encephalitis as a potential risk for durvalumab.
- Section 4.1- Clarified that global recruitment will be complete when a minimum of 80 evaluable participants have entered the maintenance phase.
- Section 4.1.2.2- Clarified that if a DLT event is observed in the safety run-in study treatment will be paused for new participants entering the maintenance phase, while the SRC convenes.
- Section 4.1.2- Divided section into 3 subheadings: Section 4.1.2.1 Maintenance Phase Overview; Section 4.1.2.2 Safety Run-In; and Section 4.1.2.2.1 Results of the Safety Run-In
- Section 4.1.2.1- Clarified that participants with disease progression should not continue treatment with durvalumab monotherapy if there are any significant, unacceptable or irreversible toxicities.
- Section 4.1.2.2- Clarified that if transition of participants to maintenance therapy is paused, patients may receive durvalumab monotherapy during the pause and will be allowed to start AZD2811 therapy after the pause if eligibility criteria are met.
- Section 4.1.2.2.1- Added summary of the results of the safety run-in cohort and associated list of proposed protocol amendments.
- Section 4.1.2.2.1- Added list of proposed protocol amendments following the results of the Safety Run-In.
- Section 4.1.2.2.1- Added that after implementation of the proposed protocol amendments in CSP v8.0, an additional safety run-in cohort will be assessed by the SRC.
- Table 9 and Table 13- Updated SC dose of filgrastim to 0.5 MU (5 µg)/kg/day and removed IV dose.
- Section 4.1.4- Changed heading to “Definition of DLT-Evaluable Participants” from previous heading of “Definition of Evaluable Patients”.
- Section 4.1.4- Corrected table number from Table 1 to Table 3.

- Section 4.3.2- Added that subsequent to the review of the safety run-in, the starting dose of AZD2811, in combination with durvalumab in the maintenance phase, has been reduced to a maximum of CCI
- Section 5.1 and Section 5.2- Changed headings to “Induction Phase Inclusion/Exclusion Criteria” from previous headings of “Inclusion/Exclusion Criteria”.
- Section 5.3.1 and Section 5.3.2- Added inclusion and exclusion criteria for maintenance phase.
- Section 6.1.2- Clarified that following permanent discontinuation of any chemotherapy agent as a result of toxicity, participants may enter the maintenance phase after consultation with the Study Physician and if they meet the maintenance phase eligibility criteria.
- Section 6.1.3- Clarified that upon initial assessment of PD, treatment with AZD2811 must be discontinued but that treatment with durvalumab may be continued until radiological PD is confirmed.
- Section 6.2.4- Clarified when CBCs should be collected and reviewed.
- Section 6.5.1.1 and Section 8.5.1- Added that AZD2811 dosing should be delayed if there is any suspicion that a patient is suffering from an infection.
- Section 6.5.1.1- Added (prophylactic) antibiotics to list of permitted concomitant medications in patients who: are experiencing Grade 4 neutropenia; are at high risk of infection; or have a suspected infection.
- Section 6.5.2.1 and Table 15- Added that herbal supplements that strongly modulate CYP3A4 must not be used during the maintenance phase.
- Section 6.6.2- Clarified that dosing may be delayed due to an immune or a non-immune-related AE and, if delayed for reasons other than treatment-related toxicity, will resume as soon as feasible.
- Section 6.6.2- Updated the period of time the durvalumab dose may be delayed for, from 6 weeks, up to a maximum of 12 weeks from initiation of corticosteroids.
- Section 8.1- Added that an unscheduled imaging assessment should be performed if disease progression is suspected.
- Section 8.2- Added that participants who enter the Maintenance Phase on durvalumab monotherapy and subsequently receive AZD2811 in a later cycle require additional safety assessments and PK sampling.
- Section 8.2.3- Corrected sentence to ‘triplicate 12-lead ECGs (about 5 minutes apart) pre- and post-AZD2811 and pre- and post-durvalumab infusion should be performed.’
- Table 17- Added footnote for CRP.

- Section 8.2.5- Added that participants will also be evaluated on CCI [REDACTED]
- Table 21- Clarified that if any toxicity does not resolve to Grade 1 or revert to baseline within 14 days, AZD2811 treatment must be discontinued.
- Table 21- Clarified that participants can only be dosed with AZD2811 on Day 1 of any Cycle if ANC is $\geq 1.5 \times 10^9/L$ and platelet count is $\geq 75 \times 10^9/L$.
- Table 21- Clarified that AZD2811 should be held until Grade 2-3 ANC or Grade 2-3 thrombocytopenia (without bleeding or requirement for platelet transfusion) has resolved and then restarted at the same dose prior to the event.
- Section 8.6.2.2- Added wording ‘will be collected’ to clarify that mandatory fresh on-treatment tumor biopsies will be collected until core biopsy samples meeting the specified criteria are received.
- Section 8.6.2.6 and Section 8.6.2.10- Added additional timepoints for collection of blood samples in line with Table 3.
- Section 9.2- Changed sample sizes.
- Table 23, Section 9.4.2.1, and Section 9.4.2.2- Clarified that only patients who received CCI [REDACTED] AZD2811 + durvalumab on CCI [REDACTED] will be included in evaluation of primary and secondary endpoints.
- Appendix F4- Updated to reflect clarifications to tumor response evaluation timepoints throughout CSP.
- Appendix H2 and Section 11- Removed reference for Silva et al, 2011.

Version 7, 29 June 2021 (Amendment 6)

- Table 21-Hematologic Toxicity criteria for neutropenic dose reductions updated to align with the Phase 1 (D6130C00001) study and associated data

Version 6, 17 May 2021 (Amendment 5)

- Tables 1-5 Schedule of Activities: Updated Notes column throughout for consistency and to improve readability
- Table 1: Removed Day -21 to Day -7 window for some labs, and clarified that screening labs should be obtained the same day as initial consent, when possible
- Tables 1 and 3; Sections 8.6.2.3-8.6.2.11: Added a note for clarity that all assessments should be performed predose, unless otherwise indicated

- Tables 1 and 3: CCI
[REDACTED]
- Tables 1, 2, 3, and 4 updated to include coagulation assessments with each safety lab visit
- Table 2: Renamed for clarity to include any participant who does not enter maintenance, and added “Survival Status/Subsequent Cancer Therapy” to the schedule of assessments.
- Tables 2 and 4: Clarified that the follow-up visit does not have to be a separate study visit; a phone call or other standard of care visit is acceptable
- Table 3: CCI
[REDACTED]
- Table 8: Updated to match treatment windows in schedule of activities and to add windows to treatment
- Table 9: Updated to add treatment windows
- Table 15: Removed wording ‘which may have immune-modulating effect’ from ‘Herbal and natural remedies’ prohibited medications.
- Table 17: Footnote C inconsistencies corrected, additional footnotes added for clarity, and Carbon Dioxide added
- Table 18: White Blood Cell Differential tests defined for clarity
- Table 19: Added required test for urine microscopy for clarity
- Sections 1.2 and 8.6.2.2; Table 3: CCI
[REDACTED]
- Added new Section 2.2.3 providing further rationale for the combination of AZD2811 and durvalumab
- Section 5.2, Exclusion #3: Clarified that culinary use of turmeric and curry is acceptable.
- Section 5.2, Exclusion #12: Clarified that if COVID-19 test is performed, the results should be reported
- Section 6.5: Added antibiotics taken within 90 days of Cycle 1 Day 1 will be recorded in the CRF
- Section 7.1.1: Moved criteria “only applies if no other anticancer therapy” as inclusion number 5, from paragraph below, for clarity.
- Appendices E1, E3, and E8: Language updated to remove references to central safety labs, as this study is using local labs only for safety assessments.

- Section 8.2.3: Clarification that sites may also report Bazett's Correction Formula (QTcB) if that is the local standard.
- Section 8.3.10 and Appendix B2: Updated “congenital abnormality” to “congenital anomaly” to align with new company standards
- Section 8.8.1: Language added to allow for use of paper back up for ePRO
- Section 9.4.2.3: Language clarified around missed RECIST assessments.

Version 5, 01 April 2021 (Amendment 4) – Italy Only

- Tables 2 and 4 updated to include additional pregnancy testing through 90 days post last dose
- Submitted as part of response to AIFA, and not submitted to any other Health Authority

Version 4, 23 February 2021 (Amendment 3) – Canada Only

- Section 5.2, Exclusion #1 language clarified to exclude history of immune mediated reactions like pneumonitis
- Section 5.2, Exclusion #8 language clarified to include pneumonitis as a type of interstitial lung disease
- Sections 4.1.1 Table 8, 4.1.2 Table 9, and 6.6.1 Table 16: Clarified observation time between infusions is elapsed time from the end of the first infusion to the start of the next infusion (or in maintenance the observation time after the end of durvalumab at the site)
- Submitted as part of response to Health Canada, and not submitted to any other Health Authority

Version 3, 04 November 2020 (Amendment 2)

- Section 5.1, Inclusion #2 language updated to “T3 or T4 tumor stage”
- Section 5.1, Inclusion #3 

- Section 5.2, Exclusion #18 was updated to clarify that this exclusion would not apply participants meeting re-treatment after relapse criteria

- Section 5.4 was updated to clarify that the maximum duration for rescreening, which must be complete within 7 weeks of initial consent
- Section 6.1.1 was updated to clarify that participants must be eligible to receive both durvalumab and AZD2811 to enter the maintenance phase
- Section 6.5 [REDACTED]
- Section 8.2.4 moved language from 8.5.1 regarding holds due to ANC and platelet counts, also clarifying that Day 1 treatment may be delayed up to 14 days for a maximum cycle length of 35 days
- Section 8.5.1 was updated to clarify that Day 1 of a cycle may be delayed up to [REDACTED] days, for a maximum cycle length of [REDACTED]. It was also updated to clarify that the cycles are calibrated to have Day 1 always be the day that the patient received study treatment. Additionally, toxicity resolution language was updated state that toxicities should be resolved to Grade 1 or baseline for consistency
- Section 8.6.2.1 [REDACTED]
- Appendix A5 was updated to change the SRC Chair from the International Coordinating Investigator to the Study Physician
- Updated randomized vs. enrolled vs. assigned to treatment language for clarity and consistency throughout
- Administrative changes for clarity and consistency throughout

Version 2, 02 November 2020 (Amendment 1) - United States Only

- Section 4.1.3 (DLT criteria) was updated to include Grade 4 anemia and any febrile neutropenia as DLTs
- Section 5.2 (Exclusion Criteria) was updated to clarify that prophylactic cranial irradiation (PCI) is allowed but must be completed before first dose of study medication
- Sections 5.2 (Exclusion Criteria) and 6.5.2.1 (Prohibited Concomitant Medication for AZD2811) were updated to exclude clinical inhibitors of BCRP during the safety run-in

- Section 8.5.2 (Specific Toxicity Management and Dose Modification Information - Durvalumab) was updated to specifically indicate that, in the US, dose modifications for durvalumab should be consistent with recommendations in the USPI.

Version 1, 01 September 2020 (Original Protocol)

Initial creation

TABLE OF CONTENTS

TITLE PAGE	1
VERSION HISTORY	3

1 PROTOCOL SUMMARY

1.1 Synopsis

Protocol Title: A Phase II, multicenter, open-label, single arm study to determine the efficacy, safety, and tolerability of AZD2811 and durvalumab combination as maintenance therapy after induction with platinum-based chemotherapy combined with durvalumab, for the first-line treatment of patients with extensive stage small-cell lung cancer.

Short Title: Phase II maintenance study of AZD2811 + durvalumab in ES-SCLC.

On 14 December 2021, AstraZeneca took the decision to terminate enrolment for this study prior to completion due to the evolving benefit risk profile of AZD2811 that does not support further development for the first-line treatment of patients with extensive stage small-cell lung cancer. Patients already enrolled in the study were able to continue. However, no further patients were permitted to start AZD2811 treatment and ongoing patients transitioning into the maintenance phase after this date were offered durvalumab monotherapy. As a result of the early termination, the data cut-off for the final analysis in this study is planned for 18 June 2022.

Sections from CSP v8.0 are retained throughout this protocol for reference. Clinical Study Protocol v8.0 was prepared to include urgent safety measures via a Dear Investigator Letter; however, CSP V 8.0 was not implemented due to early termination. Clinical Study Protocol v8.0 is superseded by CSP v9.0.

Rationale: Despite improved efficacy in the treatment of extensive stage small-cell lung cancer (ES-SCLC) resulting from the addition of programmed cell death-ligand 1 immunotherapy to platinum-etoposide, there remains an urgent need for therapies that prolong progression-free survival and overall survival in this disease. Preliminary clinical data suggest that AZD2811 may be effective in stabilizing disease in later line SCLC patients. This trial will investigate whether a similar benefit can be demonstrated in first line SCLC patients treated with AZD2811 plus durvalumab maintenance therapy, following CCI [REDACTED] of durvalumab plus platinum-etoposide induction therapy.

Objectives and Endpoints

Objectives	Endpoints
Primary	
To evaluate the efficacy of AZD2811 + durvalumab by assessment of the proportion of participants alive and progression free at 12 months (APF12) who have not progressed during etoposide and platinum-based chemotherapy (EP)-durvalumab based induction therapy.	The proportion of participants APF12 will be defined as the Kaplan-Meier estimate of progression-free survival (PFS) per Response Evaluation Criteria in Solid Tumors (RECIST) v1.1 as assessed by the investigator at local site at 12 months, in participants who enter the maintenance phase.

Objectives	Endpoints
Secondary	
To evaluate efficacy of AZD2811 + durvalumab by assessment of the proportion of participants alive at 12 months (OS12), 15 months (OS15), and 18 months (OS18), who have not progressed during EP-durvalumab based induction therapy.	The proportion of participants OS12, OS15, and OS18 will be defined as the Kaplan-Meier estimate of overall survival (OS) at 12 months, 15 months, and 18 months, respectively, in participants who enter the maintenance phase.
To evaluate efficacy of AZD2811 + durvalumab by assessment of the proportion of participants alive and progression free at 6 months (APF6) and 9 months (APF9) who have not progressed during EP-durvalumab based induction therapy.	The proportion of participants alive and progression free at APF6 and APF9 will be defined as the Kaplan-Meier estimate of PFS per RECIST v1.1 as assessed by the investigator at local site at 6 months and 9 months, respectively, in participants who enter the maintenance phase.
To evaluate efficacy of EP-durvalumab by assessment of objective response rate (ORR) in the induction phase.	ORR is defined as the proportion of participants with measurable disease at baseline who have a confirmed complete response (CR) or partial response (PR), by the investigator at local site per RECIST v1.1 in the induction phase (all participants).
To evaluate efficacy of AZD2811 + durvalumab by assessment of ORR in the participants who had not progressed during EP-durvalumab based induction therapy.	ORR is defined as the proportion of participants with measurable disease at baseline who have a confirmed CR or PR, by the investigator at local site per RECIST v1.1, in participants who enter the maintenance phase.
To evaluate efficacy of AZD2811 + durvalumab by assessment of PFS in participants who had not progressed during EP-durvalumab based induction therapy.	PFS is defined as time from date of first dose study intervention in the induction phase until progression per RECIST v1.1 or death due to any cause. The median Kaplan-Meier estimate in participants who enter the maintenance phase.
To evaluate efficacy of AZD2811 + durvalumab by assessment of OS in participants who had not progressed during EP-durvalumab based induction therapy.	OS is defined as time from date of first dose study intervention in the induction phase until the date of death due to any cause. The median Kaplan-Meier estimate in participants who enter the maintenance phase.
To assess the safety and tolerability profile of study intervention in small-cell lung cancer (SCLC).	Safety and tolerability will be evaluated in terms of adverse events, vital signs, physical examination, clinical chemistry, thyroid-stimulating hormone, prothrombin time /partial prothrombin time /international normalized ratio, hematology, electrocardiograms, and urinalysis, as well as treatment delays, dose reductions, and dose discontinuations.
To evaluate the pharmacokinetics of durvalumab and AZD2811.	Concentration of durvalumab, and AZD2811 and its metabolite in serum and whole blood, respectively.
To evaluate the effect of AZD2811 + durvalumab on SCLC symptoms and health-related quality of life (QoL) using European Organization for Research and Treatment of Cancer (EORTC) 30-item Core Quality of Life Questionnaire (QLQ-C30) and 13-	EORTC QLQ-C30: Symptoms (fatigue, pain, nausea/vomiting, dyspnea, loss of appetite, insomnia, constipation, and diarrhea). Health-related QoL/functioning (physical function, role function, emotional function, cognitive function, social function,

Objectives	Endpoints
item Lung Cancer Quality of Life Questionnaire (QLQ-LC13).	and global health status/QoL). EORTC QLQ-LC13: Disease-related symptoms (dyspnea, cough, hemoptysis, chest pain, arm/shoulder pain, and other pain).

For Exploratory objectives and endpoints, see Section 3.

Overall Design

This is a Phase II, multicenter, open-label, single arm study in ES-SCLC treatment naïve patients who do not progress per Response Evaluation Criteria in Solid Tumors (RECIST) v1.1 after induction with etoposide and platinum-based chemotherapy-durvalumab.

Participants will be treated for CCI [REDACTED] on an every CCI [REDACTED] schedule in an induction phase with platinum-based induction therapy (cisplatin or carboplatin plus etoposide) + durvalumab. At the end of this induction period, participants will be assessed for disease progression, per RECIST v1.1.

Participants who have not progressed per RECIST v1.1 at the end of the induction phase will continue into the maintenance phase of the trial following confirmation of maintenance phase eligibility criteria.

The maintenance phase will commence with a safety run-in period, in which approximately six participants will be followed for (at least) one cycle, to assess safety of the AZD2811 + durvalumab combination in order to provide the earliest opportunity to assess tolerability of the combination in those approximately six participants. After the completion of \geq CCI [REDACTED] (\geq 1 cycle) dosing in the first 6 evaluable participants, all safety data (including, but not limited to, dose-limiting toxicities, adverse events of special interest, laboratory safety assessment, vital signs, and physical examination), will be assessed to judge if the combination is safe and tolerable. This assessment, and subsequent recommendation to continue dosing in the maintenance phase, will be undertaken by a Safety Review Committee (SRC). Participants will be treated with AZD2811 + durvalumab as maintenance therapy until confirmed progressive disease, start of non-protocol defined anticancer therapy, unacceptable toxicity, or withdrawal of consent.

Disclosure Statement: This is an open-label treatment, single arm study.

Number of Participants:

Approximately 100 participants will be assigned to treatment to achieve 80 evaluable participants having received maintenance therapy.

From Clinical Study Protocol (CSP) v8.0 onwards, the starting dose of AZD2811 in the

maintenance phase will be CCI [REDACTED], the study will seek to achieve 80 evaluable participants on that starting dose.

Note: “Enrolled” means a participant’s, or their legally acceptable representative’s, agreement to participate in a clinical study following completion of the informed consent process.

Potential participants who are screened for the purpose of determining eligibility for the study, but are not assigned in the study, are considered “screen failures”, unless otherwise specified by the protocol. “Assigned” means that a participant has completed the screening period and has received at least one dose of study treatment.

Intervention Groups and Duration: A single group of participants will be treated as follows:

[figure not shown]
- Screening: Days -21 to Day -1
- Induction Phase: CCI [REDACTED] to CCI [REDACTED]
 - Durvalumab CCI [REDACTED]
 - Carboplatin (area under the curve 5 to 6) or cisplatin (75 to 80 mg/m²) CCI [REDACTED]
 - Etoposide (80 to 100 mg/m²) on CCI [REDACTED]
- Maintenance Phase: CCI [REDACTED] to confirmed disease progression
 - AZD2811 (CCI [REDACTED] with mandatory granulocyte colony stimulating factor on/from CCI [REDACTED])
 - Durvalumab (CCI [REDACTED])

Data Monitoring Committee: A SRC will be used to assess the participants in the safety run-in.

Statistical Methods: The study is single arm so there will be no formal statistical hypotheses. The analysis for the study will be descriptive.

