4.1.2 Maintenance Phase

4.1.2.1 Maintenance Phase Overview

Participants who have not progressed per RECIST v1.1 at the end of the induction phase and who meet maintenance phase eligibility criteria will continue into the maintenance phase of the trial and be treated with AZD2811 + durvalumab as maintenance therapy (Table 9) until radiological progressive disease (PD), unless there is unacceptable toxicity, withdrawal of consent, or another discontinuation criterion is met (Section 7.1).

Table 9 Study Intervention During the Maintenance Phase

Day and order of administration in each cycle	Agent and dose	Route	Duration	Observation time	Schedule
CCI	AZD2811 CCI ^a	IV	CCI		
	Durvalumab CCI	IV			
	Filgrastim 0.5 MU (5 µg)/kg/day SC from CCI (DAILY until at least CCI of each cycle AND the ANC has recovered to $\geq 1.5 \times 10^9/L$) or Neulasta (pegfilgrastim) 6 mg dose SC on CCI only	SC			

^a Dose reduction levels are provided in Section 6.6.1

^b Participants are treated until PD unless there is unacceptable toxicity, withdrawal of consent, or another discontinuation criterion is met

ANC = absolute neutrophil count; G-CSF = granulocyte colony stimulating factor; IV = intravenous; MU = million units; N/A = not applicable; PD = progressive disease; CCI [REDACTED]; SC = subcutaneously.

Hematopoietic growth factors (short-acting granulocyte colony stimulating factor [G-CSF] [filgrastim] or long-acting G-CSF [pegfilgrastim]), must be administered as primary prophylaxis on/from CCI [REDACTED] of every maintenance cycle to limit the duration of neutropenia, and to minimize the risk of neutropenic fever and infections. If short-acting G-CSF (filgrastim) is used, administer DAILY until at least CCI [REDACTED] of each cycle AND the ANC has recovered to $\geq 1.5 \times 10^9/L$. Long-acting G-CSF should be administered once only per cycle on CCI [REDACTED]

For all participants who are treated through progression with durvalumab monotherapy, the investigator should ensure participants do not have any significant, unacceptable, or irreversible toxicities that indicate continuing treatment would not further benefit the participant. AZD2811 must not be administered through progression.

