6.1.3 Duration of Treatment and Criteria for Treatment After Initial Assessment of PD

Maintenance treatment will start on CCI [REDACTED]. Participants who do not have any evidence of radiological disease progression during the induction phase (CCI [REDACTED] of EP-durvalumab)

and who meet maintenance phase eligibility criteria (see Section 5.3) will continue into the maintenance phase of the trial.

In the rare instances when the RECIST v1.1-defined radiological findings are considered equivocal by the investigator or there is doubt whether or not there is evidence of objective progression (e.g., technical issues, including image artifacts), the participant may not move into the maintenance phase of the study without prior discussion with the Sponsor.

Upon initial assessment of PD, treatment with AZD2811 must be discontinued. Treatment with durvalumab may be continued until radiological PD is confirmed by the subsequent scan, unless there is unacceptable toxicity, withdrawal of consent, or another discontinuation criterion is met. Participants with rapid tumor progression or with symptomatic progression that requires urgent medical intervention (e.g., central nervous system [CNS] metastasis, respiratory failure due to tumor compression, or spinal cord compression) will not be eligible to continue study treatment. All efforts should be put in place to perform a disease assessment to document this disease progression.

Post final data cut-off

Participants who are receiving treatment at the time of DCO can either choose to discontinue from the study or, when the investigator believes participants are gaining clinical benefit, may continue to receive study treatment, following discussion with, and approval from, the AstraZeneca Study Team. For participants continuing to receive study treatment following the final DCO and database closure assessments will revert to standard of care.

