At the end of the induction phase, participants will be assessed for disease progression per RECIST v1.1. All participants who have not progressed will be treated with AZD2811 + durvalumab or durvalumab monotherapy as maintenance therapy until confirmed radiological PD, unless there is unacceptable toxicity, withdrawal of consent, or another discontinuation criterion is met.

Follow-up Period

Period from participant's last dose of any study intervention until end of study.

Demographic data

Characteristics of the participants, including medical history and disease characteristics at baseline, will be listed for each participant and summarized where appropriate.

Exposure

Exposure to study intervention, ie, total amount of study drug received, will be listed for all participants.

Total treatment duration will be summarized by the following: Mean, standard deviation, minimum, maximum, median, and number of observations. In addition, the number and percentages of participants with at least one dose interruption and at least one dose reduction will be presented separately for the planned length of Cycle 1, defined as CCI [REDACTED], and for any time following this initial phase of study. The number of cycles of each study drug will be summarized. Participants are counted as receiving a cycle of study drug as soon as any infusion has started in that cycle.

Dose intensity data will be summarized using medians and quartiles, as well as the minimum and maximum values.

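### The Synopsis and Sections 6.1.3 and 4.1.2.1 of the protocol give different stop points for AZD2811 at disease progression and must be reconciled

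*Protocol*

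**What the plan says.** Three places in the current protocol state when AZD2811 stops in relation to progression.

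- **Synopsis (1.1), Overall Design.** The sentence names both agents: "Participants will be treated with AZD2811 + durvalumab as maintenance therapy until confirmed progressive disease". The full set of end points it gives is "until confirmed progressive disease, start of non-protocol defined anticancer therapy, unacceptable toxicity, or withdrawal of consent". Nothing in that list refers the reader to other discontinuation criteria.
- **Section 6.1.3**, which is written for treatment after progression is initially seen, separates the agents. For AZD2811: "Upon initial assessment of PD, treatment with AZD2811 must be discontinued". For durvalumab: "Treatment with durvalumab may be continued until radiological PD is confirmed by the subsequent scan".
- **Section 4.1.2.1** has the sentence that corresponds to the Synopsis. It runs the combination to radiological progression without requiring confirmation and allows for other discontinuation criteria. It then adds: "AZD2811 must not be administered through progression".

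Appendix F (F 4.1 and F 5) defines confirmation. Progression is confirmed only when two consecutive assessments meet the criteria for it. The second scan is taken at least 4 weeks after the initial one and no later than the next regular imaging visit.

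**The concern.** In this protocol, confirmed progression is a defined, later event than initial progression. A site that works from the Synopsis would read that AZD2811 and durvalumab both continue until the second scan. A site that works from Section 6.1.3 would read that AZD2811 ends at initial progression and durvalumab alone may go on. Both cannot be followed for a participant whose first scan shows progression.

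An unambiguous stop rule matters for this agent. Enrolment was ended because of its evolving benefit-risk profile, and Section 4.1.2.2.1 reports two fatal serious adverse events that investigators attributed to it. Participants already enrolled could continue, and Sections 4.4 and 6.1.3 allow study treatment after the data cut-off, when assessments revert to local standard of care.

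**Working it through.** There is no sample size, power or event-count figure to reproduce. The check is a comparison of the text, followed by scan-interval arithmetic.

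**Step 1: the passages side by side**

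| Place | AZD2811 stops at | Durvalumab stops at | Other discontinuation criteria brought in? |
|---|---|---|---|
| Synopsis, Overall Design | Confirmed progression | Confirmed progression | No |
| Section 6.1.3 | Initial assessment of progression | May run to the confirming scan | Yes, in the durvalumab sentence |
| Section 4.1.2.1 | Radiological progression; not given through progression | May be given through progression as monotherapy, subject to a toxicity check | Yes |

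**Step 2: are initial and confirmed progression the same event?** No. Appendix F 5 requires two consecutive assessments. Appendix F 4.1 and Section 8.1 place the second no sooner than 4 weeks after the first and no later than the next scheduled imaging visit.

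**Step 3: how far apart are the two stop points?** The inputs are the 4-week minimum (Section 8.1, Appendix F 4.1) and scans every 6 weeks to Week 36 and every 8 weeks after that, each ±1 week (Section 4.1, Appendix F 4.1). It is assumed that progression is first seen at a scheduled scan.

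- Earliest: 4 × 7 = 28 days.
- Latest on the 6-weekly schedule: nominally 6 × 7 = 42 days. With the first scan a week early and the next a week late, 42 + 7 + 7 = 56 days (for example, the Week 30 scan at Week 29 and the Week 36 scan at Week 37).
- Latest on the 8-weekly schedule: nominally 8 × 7 = 56 days. With both windows used, 56 + 7 + 7 = 70 days (for example, the Week 36 scan at Week 35 and the Week 44 scan at Week 45).

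These are intervals between scans. They do not measure AZD2811 exposure.

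**Step 4: does any planned analysis use the stop rule?** No dependence was found. Protocol Section 9.4.2.3 and SAP Section 3.2.2.1 count PFS regardless of withdrawal from treatment, and efficacy is now listed only. SAP Section 3.1.3 ends the maintenance phase at the later of the two agents' end dates. SAP Section 3.2.1.5 takes the intended dose up to the actual last day of dosing.

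**The case against.** The strongest reply is that the protocol as a whole does not leave AZD2811 open after initial progression. Table 3, Sections 4.1 and 8.1, and Appendix F 4.1 require scan results to be reviewed for absence of progression before AZD2811 is dosed. Section 4.1.2.2.1 also lists, among the measures proposed after the safety run-in, withholding the drug on suspicion of progression. Once a scan shows progression, the pre-dose check cannot be met, whatever the Synopsis says. This stands, and it is the main reason the practical risk is low. It does not make the Synopsis sentence agree with Section 6.1.3.

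A second reply is that a Synopsis only abbreviates, and that version 8.0 text is expressly kept for reference. But the Synopsis sentence does more than shorten. It adds the requirement for confirmation and drops the reference to other criteria, both of which set it apart from its counterpart in Section 4.1.2.1. Neither it nor Section 6.1.3 is marked as reference-only, and both stand in version 9.0.

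A reader might also infer that the same defect runs through the protocol. The documents do not support that:

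- The Synopsis entry "Maintenance Phase: CCI [REDACTED] to confirmed disease progression" describes phase length. It fits Section 6.1.3, because durvalumab may run to confirmation.
- Section 9.4.1 says participants "will be treated with AZD2811 + durvalumab or durvalumab monotherapy as maintenance therapy until confirmed radiological PD", but it carries the clause on other discontinuation criteria.
- Section 7.1 lists confirmed radiological progression as a reason to end all study intervention. That is compatible with AZD2811 having stopped earlier.
- Appendix F 4.1 and F 5 do not name the agent that may continue after initial progression, but Sections 4.1.2.1 and 6.1.3 supply it. The clinical-benefit end point in F 5 concerns how long treatment may run after progression, which is a separate question.

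**Conclusion.** The contradiction is real, lies in current text, and is limited to the Synopsis (Overall Design) against Sections 6.1.3 and 4.1.2.1. The stop points differ by at least 28 days and at most the time to the next scheduled scan, which is 70 days at the extreme of the windows under the assumption stated above.

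Severity is minor. Besides the pre-dose scan review, only 9 participants received the combination (Section 9.4), and no one could start AZD2811 after 14 December 2021 (Section 4.1).

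Two stronger readings should be resisted. One is that participants received AZD2811 for 28 to 70 days after progression. The documents do not say how many remained on AZD2811 or progressed on it, and the pre-dose review argues against it. The other is that the ambiguity contributed to the fatal events. Nothing in the documents links them to dosing after progression. The Dear Investigator Letter is not among the documents, so whether sites held separate instructions is unknown.

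**What to change.** Reconcile the Overall Design sentence of the Synopsis with Sections 6.1.3 and 4.1.2.1, so that one stop point for AZD2811 is stated throughout. Which rule is right is a decision for the sponsor's clinical team, and this review takes no position on it. Once the rule is settled, check the maintenance-phase entry in the Synopsis, Section 7.1, Section 9.4.1 and Appendix F (F 4.1 and F 5) for consistency with it. They need changing only if they then disagree.

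The cost is a wording edit within the three conflicting passages, plus that check. No data, procedures or analyses change.
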